## 8.1.3.2 Model 1: Timeliness of access to paediatric intensive care

Timeliness of access to paediatric intensive care will be measured by:

- a) Time from acceptance of the referral by a PICRT to arrival of the PICRT at the patient bedside, and
- b) Time from acceptance of the referral by a PICRT to arrival of the patient on the PICU.

## 8.1.3.3 Model 2: Care delivered by the PICRT

Three aspects of care delivered by the PICRT will be studied:

- a) Team composition: grade of PICRT team leader (consultant, junior doctor, advanced nurse practitioner); seniority of transport nurse; presence of medical technician on transport.
- b) Interventions performed by the transport team (airway-related: intubation, reintubation; vascular access: central venous, arterial, intraosseous; chest drain; use of vasoactive agents; non-invasive ventilation).
- c) Occurrence of a critical incident during transport.

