#### 8.1.3.1 Clinical outcomes

Primary outcome: Mortality within 30 days following PICU admission (the first admission in case of multiple PICU admissions), established by data linkage with death registrations.

Secondary outcomes to include:

- a) Mortality at fixed time-points (PICU discharge, 90 days and 1 year following [first] PICU admission)
- b) Number of PICU admissions during study period and time to readmission (if applicable)
- c) Length of stay in PICU (number of days from PICU admission to discharge, for each PICU admission)
- d) Resource use in PICU (number of days of invasive ventilation, vasoactive agent therapy, renal replacement therapy and extra-corporeal life support during PICU stay, for each PICU admission)
- e) Length of hospital stay linked to the first PICU admission (number of days from hospital admission to hospital discharge)
- f) Number of A&E attendances in the 12 months following discharge from the first PICU admission
- g) Hospital resource use (total number of days admitted to hospital) in the 12 months following discharge from the first PICU admission.

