1) Identifying potential confounding variables and selection of variables for model development In the first instance, we will draw upon the expertise of clinical applicants and PICANet to generate a list of potential confounding factors. We expect the main confounding variables to be severity of illness (main diagnosis leading to PICU admission, ventilation status at referral and the Paediatric Index of Mortality 2 score) and the receipt of intensive care interventions prior to the PICRT arriving at the patient bedside. Intensive care interventions carried out by the general hospital team prior to the arrival of the PICRT are recorded in PICANet; we will also include as confounders the time spent at general hospital prior to being referred/accepted for transport to PICU (from linked HES data), and care provided in an adult intensive care unit (from linked CMP data). We will seek additional input from clinical applicants at monthly PMG meetings during months 4-12 of the project to further refine this list. We have also scheduled a Study Steering Committee (SSC) meeting during months 4-6, at which clinical members (medical/nursing/allied health professionals) will help further refine the list of confounders. In this way, we will obtain extensive expert clinical input into the choice of potential confounding variables that could be included in the model development; we will also generate clinical knowledge regarding the mechanisms by which variables may influence the exposure status and outcome.

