## 2) Draw inferences regarding the effect of key factors on patient outcome

Before any modelling work is undertaken, we will do a thorough descriptive analysis of the datasets and look for potential issues that would need to be addressed at an early stage, such as a large proportion of missing data for key confounders or an unusual distribution of age/weight/diagnosis or other risk factors. Prior to multivariate modelling, we will explore univariate associations between key explanatory variables (timeliness, care delivered) and potential confounders with our stated primary and secondary outcomes. All explanatory variables and confounders with significant univariate association with outcome will be considered in the regression modelling for Models 1 and 2. We will develop statistical models to study the association between timeliness of access to intensive care and clinical outcomes, and the association between care delivered by PIC retrieval teams and clinical outcomes. Since we recognise that the data could potentially be clustered by PICRT, we will develop multilevel models as appropriate (to include the random effects of PICU/PICRT/general hospital) depending on the outcome:

- Mortality at fixed time-points: logistic regression
- Length of stay (PICU, hospital), resource use in PICU and hospital resource use following
   PICU discharge: linear, Poisson or negative binomial regression models (as appropriate) and survival models
- A&E attendances: Poisson or negative binomial regression model (as appropriate)

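### Model 2(b) relates PICRT intubation and vasoactive use to days on those same treatments, and screens interventions on a comparison that ignores treatment before arrival

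*Protocol*

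**What the plan says.** **Exposure.** Protocol 8.1.3.3, item (b), is "Interventions performed by the transport team (airway-related: intubation, reintubation; vascular access: central venous, arterial, intraosseous; chest drain; use of vasoactive agents", with non-invasive ventilation also listed. No reference group is stated.

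**Outcome.** Protocol 8.1.3.1, secondary outcome (d), is "Resource use in PICU (number of days of invasive ventilation, vasoactive agent therapy, renal replacement therapy and extra-corporeal life support during PICU stay".

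**How they are joined.** Protocol 8.1.3.4, step 2, says that before multivariate modelling "we will explore univariate associations between key explanatory variables (timeliness, care delivered) and potential confounders with our stated primary and secondary outcomes". Variables with a significant univariate association are the ones then considered for Models 1 and 2. The list of regression types includes "Length of stay (PICU, hospital), resource use in PICU and hospital resource use following" PICU discharge. No exposure-outcome pair is excepted.

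**Adjustment.** Step 1 of the same section names "the receipt of intensive care interventions prior to the PICRT arriving at the patient bedside" as a main confounder, alongside the diagnosis and "ventilation status at referral and the Paediatric Index of Mortality 2 score". It adds that "Intensive care interventions carried out by the general hospital team prior to the arrival of the PICRT are recorded in PICANet". Step 2 then has candidate models carry different sets of confounders and uses AIC to choose among them. The detailed confounding strategy is left to the SAP.

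**The concern.** There are two separate problems.

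1. **Overlap of exposure and outcome.** The treatment that defines the exposure is the treatment whose days are counted as the outcome. This is not confounding, so confounder adjustment, propensity scores and instruments are not designed to cure it.
2. **The screen.** In a univariate comparison, children for whom the PICRT did not perform an intervention include both those already treated by the referring hospital and those never treated. These groups can differ in opposite directions from the children the PICRT treated, so a real contrast can cancel before any adjusted model is fitted.

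The results have downstream uses. Section 8.4.1 expects workstream A to show which factors drive outcome, and gives bedside interventions by the PICRT as one example. Section 5.1 lists evidence for future clinical standards as an aim. An association that is partly definitional could be read as a finding about what retrieval teams do.

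**Working it through.** The protocol gives no figure that tests this point; its only power calculation (9685 transports, 8.1.3.5) concerns Model 1. The check therefore sets the sections side by side and uses two illustrations with assumed inputs.

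**Step 1: the overlapping pairs**

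| Exposure in 8.1.3.3(b) | Outcome in 8.1.3.1(d) | Overlap |
|---|---|---|
| Intubation by PICRT | Days of invasive ventilation | Yes |
| Vasoactive use by PICRT | Days of vasoactive therapy | Yes |
| Non-invasive ventilation by PICRT | Days of invasive ventilation | No: a different treatment is counted |
| Any item in (b) | Mortality, readmission, A&E attendances | No |

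**Step 2: does the planned adjustment remove the overlap?** Simulation, all inputs assumed:

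- Severity S is standard normal. The probability of needing intubation before PICU is 1/(1 + exp(−(0.5 + 1.2S))).
- Of children in need, a share q is intubated by the referring team and the rest by the PICRT.
- Ventilator days are 1 + Poisson(exp(1.2 + 0.3S)) for children in need. A share r of the others is ventilated later, with 1 + Poisson(exp(1.0 + 0.3S)) days; the remainder have 0.
- Who intubates has no effect on days.

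Central case (q = 0.75, r = 0.2): 44.6% were intubated before arrival, 15.0% by the PICRT and 40.4% not before PICU. Mean days were 4.85, 4.85 and 0.68. The pooled comparator mean is (0.446 × 4.85 + 0.404 × 0.68)/0.850 = 2.87, so the crude difference is 4.85 − 2.87 = 1.98 days.

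Apparent effect of PICRT intubation on ventilator days, by linear regression:

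| Analysis | Central case | Range over q = 0.5, 0.75, 0.9 and r = 0, 0.2, 0.4 |
|---|---|---|
| Crude, PICRT v rest | 1.98 | 1.57 to 2.79 |
| Adjusted for severity | 1.34 | 0.97 to 2.02 |
| Adjusted for severity and pre-arrival ventilation | 3.47 | 2.73 to 4.20 |
| Only children not ventilated before arrival, adjusted for severity | 3.78 | not run |
| PICRT v referring team, only children intubated before PICU, adjusted for severity | 0.01 | −0.02 to 0.04 |

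Adjusting for pre-arrival ventilation raises the figure because it takes the already-treated children out of the comparison, leaving treated against untreated. Restricting to children not yet ventilated does the same. Only the comparison by who performed the intubation returns the true value of zero. Vasoactive use was not simulated; the same reasoning applies.

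**Step 3: the univariate screen, for mortality.** Assumed mix: 60% intubated before arrival (mortality 9%), 15% by the PICRT (7%), 25% never (2%).

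- Overall: 0.60 × 9 + 0.15 × 7 + 0.25 × 2 = 6.95%, in line with the approximate 7% in 8.1.3.5.
- Pooled comparator: (0.60 × 9 + 0.25 × 2)/0.85 = 5.9/0.85 = 6.9%. The screen sees 7% v 6.9%.
- Among children not already intubated: 7% v 2%.

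**Step 4: the same mix with the planned adjustment.** No child intubated before arrival can also be first intubated by the PICRT. A model with terms for both therefore estimates the PICRT term from 7% v 2% alone. The pooling disappears once that term is in the model, and returns if model selection drops it.

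**The case against.** The strongest reply is that step 1 of 8.1.3.4 already names interventions received before PICRT arrival as a main confounder and says they are recorded. This also covers children intubated while waiting, whom ventilation status at referral would miss. The reply stands for mortality, as step 4 shows. It does not reach the two overlapping pairs, where that adjustment makes the apparent effect larger.

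Second, the univariate step is described as exploratory, and reference groups are ordinary SAP content. It is fair that the missing reference group is not in itself a fault of the protocol. But the exposures, the outcomes, their crossing and the use of univariate significance to decide what is considered are fixed here.

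A reader might infer more than the documents support:

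- **That no valid comparator exists.** One can be built from recorded data, by who delivered the intervention or among children not yet treated.
- **That PICRT intubation adds at least one ventilator day by definition.** This fails against the pooled comparator: in the assumed mix, 60/85 = 71% of it is already intubated. A floor of about one day applies only against never-ventilated children.
- **That Model 2 as a whole, or the primary outcome, is circular.** The overlap does not touch mortality, team composition or critical incidents.
- **That non-invasive ventilation is circular too.** Outcome (d) counts invasive ventilation only.

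**Conclusion.** The point holds in a limited form. As written, the protocol produces two secondary contrasts, intubation with ventilation days and vasoactive use with vasoactive days, that are partly true by construction against untreated children, and its planned adjustment does not remove this. It also lets a comparison unconditioned on prior treatment influence which interventions go forward, with later conditioning left open to AIC selection.

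The sizes (1.6 to 2.8 days crude, 2.7 to 4.2 adjusted; 7% v 6.9% against 7% v 2%) come from assumed inputs. They show the direction and mechanism and do not estimate the bias in this dataset. The simulated figures are spurious as effects of PICRT delivery; they do not measure what intubation itself does. The structural point rests on one premise: a child given the treatment by the PICRT normally arrives on it.

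The change is worth making before analysis. It does not call the primary outcome into question.

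**What to change.** In 8.1.3.3 and 8.1.3.4:

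1. Label intubation with ventilation days, and vasoactive use with vasoactive days, as descriptive only. Alternatively, replace each with a comparison of PICRT against referring-team delivery among children who received the intervention before PICU admission.
2. For the other outcomes, restrict to or condition on pre-arrival treatment status for each intervention, using the PICANet record. For reintubation, include only intubated children. Apply this in the univariate step and in every Model 2(b) fit.
3. Keep the pre-arrival term in those models regardless of AIC.
4. State that confounding by indication remains when treated children are compared with untreated children not already on the intervention. The candidate instruments named in 8.1.3.4 (distance, service activity) bear on timeliness and not on the need for an intervention.

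The cost is wording and subsetting of data the study will already hold. Where restriction is used, each intervention analysis has fewer children and less precision.

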## 8.1.3.4 Model development

Prior to model development and data analysis, we will discuss and finalise a statistical analysis plan, which will outline the statistical methodologies to be employed during the analysis and a strategy for addressing confounding and how we will deal with missing values. A draft statistical analysis plan will be discussed at the first study steering committee (SSC) meeting during months 4-6 and finalised over subsequent months.

The overall strategy for the model development will consist of three main steps: 1) to identify potential confounding variables (both measured and unmeasured) and to select appropriate confounders available from the linked dataset for inclusion in the analyses; 2) to utilise carefully considered traditional regression models as well as propensity scores to draw inferences regarding the effect of key factors on patient outcome; and 3) to investigate the issue of unmeasured

confounding using instrumental variable analysis and perform sensitivity analyses to estimate the effects of unmeasured confounders on our findings.

1) Identifying potential confounding variables and selection of variables for model development In the first instance, we will draw upon the expertise of clinical applicants and PICANet to generate a list of potential confounding factors. We expect the main confounding variables to be severity of illness (main diagnosis leading to PICU admission, ventilation status at referral and the Paediatric Index of Mortality 2 score) and the receipt of intensive care interventions prior to the PICRT arriving at the patient bedside. Intensive care interventions carried out by the general hospital team prior to the arrival of the PICRT are recorded in PICANet; we will also include as confounders the time spent at general hospital prior to being referred/accepted for transport to PICU (from linked HES data), and care provided in an adult intensive care unit (from linked CMP data). We will seek additional input from clinical applicants at monthly PMG meetings during months 4-12 of the project to further refine this list. We have also scheduled a Study Steering Committee (SSC) meeting during months 4-6, at which clinical members (medical/nursing/allied health professionals) will help further refine the list of confounders. In this way, we will obtain extensive expert clinical input into the choice of potential confounding variables that could be included in the model development; we will also generate clinical knowledge regarding the mechanisms by which variables may influence the exposure status and outcome.

Based on the clinical knowledge generated through the above process, we will produce directed acyclical graphs (DAG) to visually examine the assumptions regarding the causal structure of the variables being analysed and to help decide which variables should be included as confounders. The visualization of the process will also help in the identification of measurable factors that might serve to block a backdoor path including an unmeasured (or unmeasurable) confounder. It will also serve to allow the effect of any likely bias induced by unmeasured confounding to be estimated. DAGs will also help differentiate confounding variables (variables that affect the outcome and have an association with the exposure status) from variables that could potentially be used as instruments in the instrumental variable analysis (variables that affect the exposure status but not the outcome, other than through the exposure). The final DAG will be derived by consensus where possible, or by a majority view of the experts involved if necessary.

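### Model 1 counts referring-hospital and adult-ICU care as confounders with no cut at referral acceptance, mixing pre-acceptance care with care that a longer wait may itself cause

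*Protocol*

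**What the plan says.** Protocol section 8.1.3.2 gives Model 1 two exposures. Measure (a) is "Time from acceptance of the referral by a PICRT to arrival of the PICRT at the patient bedside". Measure (b) continues until the child reaches the PICU. Both clocks start at acceptance.

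Step 1 of section 8.1.3.4 sets out the expected adjustment variables. It says "We expect the main confounding variables to be severity of illness", which includes "ventilation status at referral and the Paediatric Index of Mortality 2 score", and adds "the receipt of intensive care interventions prior to the PICRT arriving at the patient bedside". It explains that "Intensive care interventions carried out by the general hospital team prior to the arrival of the PICRT are recorded in PICANet". It then commits to including two further confounders: "the time spent at general hospital prior to being referred/accepted for transport to PICU" and "care provided in an adult intensive care unit (from linked CMP data").

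The list is to be refined with clinical input and a causal diagram (DAG). The same section describes a confounder as a variable that affects the outcome and is associated with exposure status, and has the diagram separate confounders from candidate instruments. Step 2 screens variables by univariate association with outcome, selects models by AIC, and promises care over confounders that could mask the effect of timeliness, with distances and PIM-2 as examples. Section 8.1.2.1 justifies the data linkage partly on the ground that pre-transport care is likely to confound the association.

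**The concern.** The intervention variable is measured up to the moment at which exposure (a) ends, so it takes in everything the referring hospital did while waiting. A child who waits longer has more time to deteriorate, be intubated, have lines placed or be moved to an adult ICU. To that extent the variable lies downstream of the exposure.

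Conditioning on it answers a different question: how delay relates to death among children who received the same care during the wait. If unmeasured severity drives both that care and death, conditioning also opens a non-causal path between delay and death.

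Section 8.1.3.5 frames the study around the contrast at 3 hours, and section 8.4.6 plans to give the workstream A associations a causal interpretation when choosing team numbers and locations. Both uses call for the total effect of delay.

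**Working it through.** The point is structural and uses none of the protocol's numerical results, so there is no planned figure to reproduce.

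**Step 1: compare the time windows.**

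| Quantity | Window closes at | Relation to the acceptance-to-bedside wait |
|---|---|---|
| Exposure (a), 8.1.3.2 | PICRT at bedside | is the wait |
| Exposure (b), 8.1.3.2 | arrival on PICU | contains the wait |
| Ventilation status, 8.1.3.4 | referral | not after the start of the wait |
| General-hospital time, 8.1.3.4 | referral/acceptance | ends by the start of the wait |
| Intensive care interventions, 8.1.3.4 | PICRT at bedside | covers the whole wait, plus earlier care |
| Adult-ICU care, 8.1.3.4 | no limit stated | can overlap the wait |

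Two covariates in the same paragraph are cut at or before the start of the clock; two are not. Section 8.1.2.1 describes adult-ICU admission for stabilisation before transport, which confirms that the overlap is possible.

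**Step 2: split the variable.** Care before bedside arrival = care before acceptance + care between acceptance and arrival. The first part precedes the exposure and can confound it. The second can be affected by it.

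**Step 3: test the written safeguards.** A mediator affects the outcome and is associated with exposure, so it meets the protocol's description of a confounder. Univariate screening and AIC both favour predictors of outcome, so neither would remove it. A carefully drawn DAG would expose it, but the text does not ask the diagram to identify variables affected by the exposure.

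**Step 4: illustrate direction.** In a simulation of 300,000 children every coefficient is an assumption; none comes from the protocol. With S standard normal severity, P pre-acceptance care, D long delay, W care during the wait and Y death:

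- logit P = −1 + 0.8S
- logit D = −1.75 − 0.3P
- logit W = −1 + aD + S
- logit Y = −3.3 + 0.25D + bW + S

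The direct delay odds ratio is exp(0.25) = 1.28. Fitted delay odds ratios, adjusting for S throughout:

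| a (delay→care) | b (care→death) | Adjusted for P only | Adjusted for P and W | One flag for any care before arrival |
|---|---|---|---|---|
| 1 | 0.5 | 1.46 | 1.33 | 1.42 |
| 1 | 1 | 1.63 | 1.33 | 1.52 |
| 1 | −0.5 | 1.19 | 1.31 | 1.23 |
| 0 | 0.5 | 1.26 | 1.26 | 1.28 |

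Each row is a single run, so the fully adjusted values scatter around 1.28. Adjustment attenuates when care during the wait goes with higher mortality, inflates when that care is protective, and does nothing when delay does not alter care. The single flag, closest to the variable as worded, moves part of the way.

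With severity left out of the model, a = 1 and b = 0, there is no mediated effect to remove. Adding W still moves the odds ratio from 1.24 to 1.07, which is collider bias.

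**The case against.** **The list is provisional.** Section 8.1.3.4 speaks of expected and potential confounders, plans further clinical input and a DAG, and leaves the strategy for confounding to a statistical analysis plan that is not at hand. This largely stands: the protocol does not bind the analysts to adjust for mediators. But the windows are written down, the linkage rationale already treats pre-transport care as confounding, and the stated definition would let a mediator through.

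**The masking caution could cover this.** Its examples are only illustrative, and PIM-2 appears both on the confounder list and among the variables that might be left out, so a listed variable is not certain to be adjusted for. This stands too, and the omission of interventions from those examples proves nothing.

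**Stronger readings that the documents do not support:**

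- A reader might infer that these variables are purely consequences of delay and should be dropped. They also hold pre-acceptance care, which is a proper confounder.
- A reader might infer that one Model 1, with one covariate set, serves both exposures. Step 2 plans several models with different combinations of confounders.
- A reader might infer that adjustment must shrink the delay effect and cost power. If half of the 3-point difference were removed, 8.5% against 7.0% with a 15:85 split and a design effect of 9685/5059 = 1.914 gives power of about 32% at 9685 transports and 45% at 15,000. The mediated share is invented. The design effect is back-solved from an assumed 7% against 10%, because no intracluster correlation is stated. Nor would it stay constant: with 10 equal teams the implied correlation is about 0.00095, the design effect at 15,000 is 1 + 1499 × 0.00095 = 2.42, and power is about 38%. The direction is itself open.

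**Conclusion.** The point holds as a modest, inexpensive correction. As worded, two Model 1 covariates mix care before acceptance with care during the wait, and adjusting for the second part departs from the total effect of delay. The bias may attenuate or inflate the estimate, or act through unmeasured severity; its size cannot be obtained from the protocol.

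The conclusion rests on two assumptions. First, waiting longer can change what the referring hospital does, which is plausible but not demonstrated in the protocol; if it does not, mediation is absent. Second, the target is the total effect. Objective 1.1 is worded as an association, but section 8.4.6 intends a causal use.

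**What to change.** Three wording changes, to be settled before modelling:

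1. In section 8.1.3.4, step 1, limit interventions and adult-ICU care to those received at or before referral acceptance in the primary, total-effect Model 1, in line with the limits already set for ventilation status and general-hospital time. Because exposures (a) and (b) start together, the same cut serves both.
2. In the DAG paragraph of that section, add that a confounder must not be affected by the exposure.
3. Report a model that also adjusts for care between acceptance and PICRT arrival, labelled as a secondary or sensitivity analysis and not as the effect of delay.

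The cost is text and splitting the linked variables by time; no new patients are needed. The protocol does not say whether interventions are time-stamped. Where they are not, only status at referral can be used, which leaves some residual severity confounding. That should be declared and examined by comparing the two models, bearing in mind that a difference between them may reflect confounding, mediation or collider bias.
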